## 3.0 Multi-Site Research Communication & Coordination

N/A

## 4.0 Research Data Source/s

### 4.1 Primary Data-Subjects and Specimens

Female patients planning for cesarean delivery at Robert Wood Johnson University Hospital

### 4.2 Subject Selection and Enrollment Considerations

#### A. Recruitment Details

Recruitment will start in July 2018 (pending IRB approval). Patients will be identified for participation in several locations. Prenatal patients at the Rutgers Medical Group Obstetrics and Gynecology or Maternal Fetal Medicine practices, or the High Risk Obstetric Perinatal Clinic will be approached for study inclusion. Physicians that have a direct treatment relationship with the patient will inform the patient about the study and invite them to enroll. The recruitment method will be a direct discussion of the study through face-to-face interactions with patients during standard prenatal care. The informing statement will closely resemble: *“We are conducting a study to see if patients recovering from a C-section will find pain relief from using a small portable machine called a TENS unit. The TENS unit is currently used as a safe method for muscle pain relief and may reduce the need for opioid medication. Would you like to participate?”* To attenuate concerns of authoritative pressure, the physician will assure the patient that their decision to participate or not participate will not impact the quality of care they receive. Consent for participation will be reviewed with the principal investigator and signed prior to delivery hospitalization. Randomization will follow consent, and patients randomized to intervention will have teaching performed about how to use the device at the time of consent.

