Following cesarean delivery, subjects will be re-approached in the Postpartum Unit at Robert Wood Johnson University Hospital by study staff. The TENS device will be again reviewed, and provided to the patient, with review of instructions for use. The patients in the intervention group will be educated on the proper way to utilize the TENS unit. They will apply the patches of the TENS unit above and below the C-section site. Specifically, the electrode patches will be placed above the abdominal bandages post-operatively and replaced above the abdominal bandages after the dressing change on post-operative day 1. Starting 8 hours after C-Section, the TENS unit will be turned on to a comfortable intensity as determined by the patient and will remain on until the patient is discharged, to be removed for toileting and showering and at the patient's discretion. Once the TENS unit is applied and turned on, the patient will not have to do anything else to maintain the therapy. Study staff will provide a record for documentation of time on/off for the unit. Additionally, a member of the study staff will check on the device daily to ensure proper maintenance. On the day of discharge, study staff will collect the device, and conduct a short survey about pain scores. They will then review pain scores, pain medication usage and other secondary outcomes in the patient's chart. Finally, pain will be reassessed at the subject's outpatient postpartum visits by study staff. The subjects will complete a measure of perceived physical disability at the outpatient postpartum visit.

**DATA COLLECTION.** Our research team members will collect the following data points from the patient's inpatient medical record: pain scale scores, medication requests/prescriptions (including name, type, and amount), time to first bowel movement, subjective incision site complaints, and time to OOB. Participants will complete a survey before discharge which will solicit additional information about the postpartum recovery experience with or without TENS therapy. (Survey is submitted with this protocol as Appendix A.) Participants will complete a survey at the 6-week postpartum visit on perceived difficulties because of health (The survey, WHODAS 2.0, is submitted with the protocol as Appendix B).

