**DURATION OF STUDY.** Study duration will be no more than 12 weeks. This will include up to 6 weeks prior to delivery for study approach and consent, delivery hospitalization, and 6 weeks postpartum for pain assessments at postpartum visits. There will be no long-term follow up.

**PRIMARY and SECONDARY ENDPOINTS.** Primary endpoint of this pilot study is a total of 10 normal patients undergoing cesarean, and 10 patients with history of opioid addiction. Intervention will be performed in 5 patients in each group. Safety data will be reviewed following the first 10 patients to evaluate for worsening patient scores relative to controls.

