##### **B. Consent Process**

- **Location of Consent Process**

Version Number: 5

Protocol Number: Pro2018001008

PI Name: [name]

Protocol Title: TENS after Cesarean Delivery

10

RESERVED FOR IRB STAMP

DO NOT MODIFY THIS SPACE

IRB ID: Pro2018001008

IRB Form Version: 01/2018 Approval Date: 7/19/2022

Expiration Date: 7/18/2023

Prenatal patients at the Rutgers Medical Group Obstetrics and Gynecology or Maternal Fetal Medicine practices, or the High Risk Obstetric Perinatal Clinic will be approached for study inclusion. Consent will occur in these locations.

■ **Ongoing Consent**

Consent will be reconfirmed following delivery prior to application of the device.

■ **Individual Roles for Researchers Involved in Consent**

[name] or [name] will obtain informed consent. [name], [name] or [name] will reconfirm consent at the time of device application.

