**B. Adults Unable to Consent / Cognitively Impaired Adults (for interventional studies)**

■ **NJ Law-Assessment of Regaining the Capacity To Consent**

If the attending clinician caring for the patient considers her able to consent for cesarean surgery, this will be considered sufficient for capacity to consent for this research trial.

■ **Capacity To Consent**

Surrogate consent will not be sought.

■ **NJ Law-Selecting A Witness**

Nursing or medical staff in the prenatal office may serve as a witness to consent if necessary.

■ **Removing a Subject**

If a patient withdraws consent at the time of cesarean or at any time of device application, no outcome data will be collected, and all study documents including consent and log of TENS

device will be destroyed by shredding. If a subject requests removal after data collection, data will be destroyed.

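### Allocation is made and disclosed at a prenatal visit and the only written reconfirmation of consent is tied to the device, so losses before TENS starts may differ by arm and leave no data

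*Protocol*

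**What the plan says.** **Before delivery.** The target group in Protocol 4.1 is "Female patients planning for cesarean delivery at Robert Wood Johnson University Hospital". On timing, 4.2.A says: "Consent for participation will be reviewed with the principal investigator and signed prior to delivery hospitalization". It continues: "Randomization will follow consent, and patients randomized to intervention will have teaching performed about how to use the device at the time of consent". The Duration of Study paragraph in 1.3 gives the window: "This will include up to 6 weeks prior to delivery for study approach and consent".

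**After delivery.** Section 1.3 has study staff re-approach subjects on the postpartum unit, without naming an arm, and goes straight on to the device: "The TENS device will be again reviewed, and provided to the patient, with review of instructions for use". TENS begins 8 hours after surgery. The unit may be taken off when the patient wishes, and time on and off is logged. On consent, 4.6.B says: "Consent will be reconfirmed following delivery prior to application of the device". It adds that named staff "will reconfirm consent at the time of device application". No equivalent step is written for controls.

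**Withdrawal.** Under Removing a Subject (4.7.B): "If a patient withdraws consent at the time of cesarean or at any time of device application, no outcome data will be collected". The consent form and device log are then shredded, and data already collected are destroyed if the woman asks to be removed.

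**Analysis.** The SAP defines no analysis population. Its missing-data statement concerns values missing at some time points, not women with no values at all.

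**The concern.** Randomisation protects the comparison only for as long as the randomised groups stay intact. Here the allocation is open from the prenatal visit. A woman may then deliver vaginally, deliver elsewhere or change her mind before treatment starts, and the protocol does not say how a randomised woman who has no cesarean at this hospital is handled. A TENS woman is also asked again, soon after surgery, whether she still agrees. As written, a control woman is not.

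If that extra question leads some TENS women to withdraw for reasons related to pain or willingness, the remaining TENS group is a selected one. A mixed model cannot recover women who have no observations. Because the study documents are destroyed and no count is required, the report might be unable to show how many women left each arm or why. The same women would drop out of the intervention/control pairs on which the suspension rule in 6.3 relies.

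The point reaches beyond these 20 women, because 1.5 presents the pilot as the basis for larger trials.

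**Working it through.** **Inputs from the documents.** Four cells of 5 (1.5): 4 × 5 = 20, which matches the total in 4.5.A and gives 10 TENS and 10 control. Section 4.5.C gives 40, a separate inconsistency; 20 is used here. Consent window: up to 6 weeks (1.3). TENS start: hour 8 (1.3). Loss rate, overall or by arm: not given, so there is no planned figure to reproduce and every rate below is an assumption.

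**Step 1: is any loss likely?** With independent loss probability q per woman, the chance that all 20 remain is (1 − q)^20, and the chance that at least one of 10 TENS women is lost is 1 − (1 − q)^10.

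- q = 5%: 0.36 and 0.40
- q = 10%: 0.12 and 0.65
- q = 20%: 0.01 and 0.89

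**Step 2: how unequal could it be?** Let c be the loss common to both arms and e an extra loss in the TENS arm only, at reconfirmation. TENS loss is t = 1 − (1 − c)(1 − e), and the TENS share of losses is t/(t + c).

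- e = 0: 50%
- c = 20%, e = 5%: t = 0.24, share 0.24/0.44 = 55%
- c = 10%, e = 10%: t = 0.19, share 0.19/0.29 = 66%
- c = 5%, e = 10%: t = 0.145, share 0.145/0.195 = 74%
- c = 0, e > 0: 100%

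The share exceeds one half whenever e > 0, but how far depends on e relative to c. The documents give neither.

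**Step 3: worst case for the estimate.** Assume normal pain levels, no true effect, controls intact, and that exactly the k highest-pain TENS women of 10 are lost. The expected order statistics of 10 standard normals sum to zero, so the mean of those remaining is minus the sum of the removed values, divided by 10 − k. The two largest expected values are 1.539 and 1.001.

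- k = 1: −1.539/9 = −0.17 SD
- k = 2: −(1.539 + 1.001)/8 = −0.32 SD

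A simulation of 400,000 samples gave −0.170 and −0.316. Losing the worst 1 of 5 within one opioid-history category gave −0.29 SD. By symmetry, losing the lowest-pain women instead gives shifts of the same size against TENS. Loss unrelated to outcome gives an expected shift of zero.

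**Step 4: is early allocation needed?** Set 4.2.A beside 1.3 and 4.6.B. Device teaching at the consent visit is repeated at the bedside after cesarean. Under Subject Understanding (4.6.B) the device can be tried at consent, and nothing there requires the arm to be known. No step before the postpartum visit, other than the early teaching itself, depends on the allocation.

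**The case against.** A reader might infer that losses will fall mainly on the TENS arm. The documents do not support that. They give no loss rate and no split by arm. Vaginal delivery and delivery elsewhere can happen in either arm and are not plausibly caused by allocation. Withdrawal at cesarean is open to controls, who may also leave once they know they will get no device. Section 1.3 re-approaches subjects in general, so a reconfirmation step for controls is unstated rather than ruled out.

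A reader might also infer that the bias must favour TENS. That is not established either. TENS is added to usual care, so women in most pain may be the keenest to use it, and women with little pain may decline it. A reluctant woman need not withdraw: she can take the unit off and still contribute chart data. Trying the device at consent may screen out unwilling women before randomisation.

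The shifts in Step 3 are a deliberate worst case on pain level. The SAP's primary analysis is mean change in VAS over the stay, which need not move by the same amount. Six weeks is the maximum of the window, not the typical interval. Finally, this is a pilot without a power analysis, and late allocation would not stop a TENS woman from withdrawing afterwards.

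All of this stands, and it limits what can be claimed about size and direction. It does not change the structure: allocation is known before delivery, the one written opt-out is linked to the device, and withdrawals leave nothing to analyse.

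**Conclusion.** The design leaves an avoidable route to unequal attrition that could not be seen in the results. Three facts carry this and need no assumption: the arm is disclosed before the delivery admission, reconfirmation of consent is written only for device application, and women who withdraw there have no outcome data and their records destroyed. Whether attrition will in fact be unequal, and in which direction it would bias the result, cannot be determined from the documents.

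The size is illustrative: about 0.17 or 0.32 SD in favour of TENS if the one or two highest-pain TENS women of 10 are lost and no controls are, and zero if loss is unrelated to outcome. This is a worthwhile and inexpensive improvement to the design. It is not evidence that the comparison is already biased.

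**What to change.** 1. Keep prenatal consent and the chance to try the device at that visit.
2. After cesarean, reconfirm consent in all women in the same way. Then open the allocation, within opioid-history category, before hour 8. Women who do not have a cesarean are then never randomised.
3. Teach TENS women at the bedside visit already planned in 1.3.
4. Late allocation does not remove later withdrawals, so keep a de-identified count of post-randomisation losses by arm, with reasons, that survives the destruction of records.
5. State in the SAP that all randomised women whose data may be used are analysed in their allocated arm, including those who stop using the device without withdrawing consent.

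Cost: a protocol amendment and a short SAP addition. TENS women lose the early arm-specific teaching, and staff must reconfirm consent and open the allocation between surgery and hour 8, whatever the time of delivery.

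The SAP is dated 7/11/2024 and is partly in the past tense. If enrolment has ended, report the numbers randomised and lost by arm as far as they can still be established, say where they cannot, and carry items 1 to 5 into the next trial.

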#### B. Source of Subjects

Patients will be identified for participation in several locations. Prenatal patients at the Rutgers Medical Group Obstetrics and Gynecology or Maternal Fetal Medicine practices, or the High Risk Obstetric Perinatal Clinic will be approached for study inclusion.

#### C. Method to Identify Potential Subjects

[name] will inform physicians and staff in the practices mentioned of the planned study. She will be contacted regarding potential patients, and be available for a prenatal visit for interested subjects.

#### **D. Subject Screening**

- Physicians that have a direct treatment relationship with the patient will inform the patient about the study and invite them to enroll. [name] will confirm eligibility thereafter.

- **Inclusion Criteria**

- Women aged between 18 and 45 years
- Understand and be able to follow written and oral instructions in English
- Provide written informed consent
- History of prior opioid addiction for half of the patients. (Opioid use will be obstetric patients on narcotic replacement with methadone or subutex.)

- **Exclusion Criteria**

History of cardiac arrhythmia or pacemaker usage

#### **E. Recruitment Materials**

N/A

#### **F. Lead Site Recruitment Methods**

N/A

#### **4.3 Subject Randomization**

A random number generator will be used for randomization, with even groups randomized to no intervention, and odd groups to intervention.

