### **1.3 Research Design and Methods**

**OVERVIEW.** This study is a pilot randomized interventional trial. Two categories of participants will be randomly assigned to an invention or control group, using a random number generator: normal cesarean without associated comorbidity, or cesarean in women with a history of opioid addiction, as defined by use of opioid replacement medications of either methadone or Subutex during pregnancy. The control group will receive usual care which is

Version Number: 5

Protocol Number: Pro2018001008

PI Name: [name]

Protocol Title: TENS after Cesarean Delivery

4

RESERVED FOR IRB STAMP

DO NOT MODIFY THIS SPACE

IRB ID: Pro2018001008

[figure not shown]
IRB Form Version: 01/2018 Approval Date: 7/19/2022

Expiration Date: 7/18/2023

standard post-operative pain management with opioids and NSAIDS. The intervention group will receive usual care plus TENS therapy beginning 8 hours after C-section and continuing to discharge. Both groups will receive medications for pain as requested or ordered by the doctor.

**RESEARCH PROCEDURES.** Patients will be identified for participation in several locations. Prenatal patients at the Rutgers Medical Group Obstetrics and Gynecology or Maternal Fetal Medicine practices, or the High Risk Obstetric Perinatal Clinic will be approached for study inclusion. Physicians that have a direct treatment relationship with the patient will inform the patient about the study and invite them to enroll. Consent for participation will be reviewed with the principal investigator and signed prior to delivery hospitalization. Randomization will follow consent, and patients randomized to intervention will have teaching performed about how to use the device at the time of consent.

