### **1.5 Sample Size Justification**

This is a pilot feasibility study to evaluate effectiveness and acceptability in our patient population of TENS use throughout delivery hospitalization. We aim to have 20 participants total: 5 in control and 5 in intervention without history of opioid addiction, and 5 in control and 5 in intervention with history of opioid addiction/misuse. This sample size is comparable to other shorter term pilot studies. This pilot study will serve as the basis for larger trials in the future, with larger sample size powered to demonstrate reduction in pain scores. We anticipate recruitment for this trial will take approximately 6-9 months.

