## **6.3 Data and Safety Monitoring**

### **A. Periodic Data Evaluation**

Data will be evaluated after pairs of intervention and control subjects are enrolled to compare differences. If 3 consecutive sets of intervention/controls demonstrate worse outcomes for intervention subjects, the study will be suspended. Additionally, interim data analysis will be performed by the project statistician after enrollment of 50% of subjects to ensure that device usage does not cause increased pain.

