TENS and Opioid Use After Cesarean Delivery

NCT03843788

Document Type: Statistical Analysis Plan

Document Date: 7/11/2024

Statistical Analysis Plan

All outcomes will be presented using descriptive statistics; normally distributed data by the mean and standard deviation (SD) and skewed distributions by the median and interquartile range (IQR).

Primary Outcome

The primary analysis will compare intervention groups (TENS vs usual care) on mean change in pain score as measured by Visual Analog Scale (VAS) over the course of the inpatient hospital stay. Measured primary outcomes were pain ratings, number and type of pain medications used, and patient satisfaction with pain control. Fixed effects repeated measures analysis of variance was used to evaluate the differences in pain scores between groups and Mann-Whitney tests were used to examine differences in medication intake. Additionally, repeated measures correlation (RMCORR) between TENS and usual care arms with an exploratory analysis of pain behavior in individuals with SUD compared to no SUD will be performed.

Secondary outcomes

Secondary outcomes will include pain surveys at 6 weeks postoperatively, time to first bowel movement, level of sedation, and time to out-of-bed (OOB).

Missing data

Mixed-effects procedure was utilized to avoid loss of data from missing values at different time points.

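### The SAP compares arms without the opioid-history category that the design balances within, and Protocol 4.3 does not say how that balance is secured

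*Protocol*

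**What the plan says.** **Design.** Protocol 1.3 defines two categories, cesarean without comorbidity and cesarean in women on methadone or Subutex during pregnancy, and says: "Two categories of participants will be randomly assigned to an invention or control group, using a random number generator". Its endpoints paragraph plans 10 women per category and adds: "Intervention will be performed in 5 patients in each group". Section 1.5 gives the cells, "5 in control and 5 in intervention without history of opioid addiction", and the same again for women with an opioid history.

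**Allocation.** Section 4.3 is one sentence: "A random number generator will be used for randomization, with even groups randomized to no intervention, and odd groups to intervention". No block, cap, balanced list or closing rule appears there or elsewhere. Section 6.3 A mentions pairs, but for data review: "Data will be evaluated after pairs of intervention and control subjects are enrolled to compare differences".

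**Analysis.** For pain, the SAP says: "Fixed effects repeated measures analysis of variance was used to evaluate the differences in pain scores between groups". For medication: "Mann-Whitney tests were used to examine differences in medication intake". It gives no list of model terms, and names no covariate or stratum for either comparison. SUD status, which I take to be the opioid-history category, appears only in an exploratory analysis of SUD against no SUD.

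**The concern.** The protocol itself treats opioid history as important. Half the sample is recruited on it (4.2 D), and pain control is expected to improve most in those women (1.1 B). An analysis that leaves out a factor on which the arms were balanced puts the between-category difference into the error term. The standard error is then too large and power is lost, even if every cell is exactly as planned.

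If the cells are not as planned, the arms differ in their share of opioid-history women, and an unadjusted estimate absorbs part of the category difference. Analysing mean change in pain removes some of any stable difference in level. Medication intake has no such protection: no change score is stated, one category is defined by opioid replacement treatment, and less opioid use is the first objective in 1.1 A.

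The second gap concerns 4.3. The protocol commits to exact cell sizes but describes no procedure that would produce them.

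**Working it through.** **The plan's own figure.** 2 categories × 2 arms × 5 = 20, as in 1.5 and 4.5 A. The documents give no power calculation, SD or category difference. Below, δ is the outcome difference between categories in within-category SDs, taken as 1 with a range of 0.5 to 1.5. This is an assumption.

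**1. Exact 5:5 cells, category omitted.**
- True standard error of the arm difference, 10 per arm: √(2/10) = 0.447 SD.
- Each arm holds 5 women from each category, so the category adds 10 × (δ/2)² = 2.5δ² to each arm's sum of squares, or 5δ² over both arms on 18 degrees of freedom.
- Reported SE ÷ true SE ≈ √(1 + 5δ²/18).

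| δ | ratio | reported SE |
|---|---|---|
| 0.5 | √1.069 = 1.034 | 0.462 |
| 1 | √1.278 = 1.130 | 0.506 |
| 1.5 | √1.625 = 1.275 | 0.570 |

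The effect on a two-sided 5% test was simulated with normal outcomes, one value per woman and 100,000 trials. Power is for an assumed 1 SD TENS effect.

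| δ | type I error, t-test without category | type I error, with category | power without | power with |
|---|---|---|---|---|
| 0.5 | 4.3% | 5.0% | 0.54 | 0.56 |
| 1 | 2.9% | 5.0% | 0.46 | 0.56 |
| 1.5 | 1.4% | 5.1% | 0.35 | 0.56 |

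The exact Mann-Whitney test behaves alike: about 2.6% at δ = 1.

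**2. Unequal cells.** The shift in the unadjusted estimate is δ × (difference between arms in opioid-history share). At a 30-point difference it is 1 × 0.30 = 0.30 SD (0.15 to 0.45), against a standard error of 0.447 SD. At a 40-point difference (7 of 10 against 3 of 10), the unadjusted Mann-Whitney false-positive rate is about 8% at δ = 1, and about 5–6% and 11% at the ends of the range.

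**3. How often cells would be unequal, if 4.3 means independent 50:50 draws (an assumption).** With 10 women per category, the number on TENS is Binomial(10, 0.5).
- 5:5 in one category: 252/1024 = 0.246. In both: 0.246² = 6.1%.
- 6:4 or better in both: 0.656² = 43.1%.
- 8:2 or worse in at least one: 1 − (1 − 0.109)² = 20.7%.
- Opioid-history share differing between arms, enumerated over all splits: by 30 points or more in 26.8%, by 40 or more in 12.4%.
- Section 4.5 C gives 40 where 4.5 A gives 20. With 20 per category, 10:10 in both occurs in 3.1% and a difference of 30 points or more in 8.1%.
- Averaged over all splits at N = 20, the unadjusted Mann-Whitney false-positive rate is 4.6% to 4.8% for δ from 0.5 to 1.5.

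**4. Permuted blocks of 2 or 4, equally likely, one list per category.**
- The chance that a block ends at woman 2, 4, 6, 8 is 0.5, 0.75, 0.625, 0.6875.
- Woman 10 falls midway through a block of 4 with probability 0.6875 × 0.5 = 0.344. One third of such half-blocks are 2:0, so 6:4 occurs in 0.344/3 = 11.5%.
- 5:5 in one category: 88.5%. In both: 0.885² = 78.4%. As allocated, never worse than 6:4.

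**The case against.** **The allocation figures rest on an assumed reading.** A random number generator can produce a balanced list per category, and the wording about groups in 4.3, the fixed count in 1.3 and the pairs in 6.3 A are all compatible with one. This stands: what the text establishes is an under-described method. A reader might infer that 4.3 shows a defective randomization that will almost never meet its target. The documents do not support that, because they do not say that the draws were independent.

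**Simple randomization is valid.** This also stands. A reader might infer systematic bias or an inflated error rate. The 8% rate applies only given a 40-point imbalance; over all splits the rate stays at or below 5%.

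**The unadjusted comparison is legitimate in a small unpowered pilot, and SUD is explored.** It is legitimate, and at 5:5 it is conservative. But an exploratory SUD comparison does not adjust the TENS contrast, and the loss of precision remains when every cell is as planned.

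**Changing the analysis now may be post hoc.** The SAP is dated 7/11/2024 and partly in the past tense, so results may be known. This stands and governs the fix.

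**Blocks have a price.** In an open trial, staff who see past assignments can anticipate some later ones, and blocks of 2 and 4 still miss 5:5 in at least one category about 22% of the time.

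**Conclusion.** The point holds, chiefly as a gap in the SAP: the design balances arms within opioid-history category, and the stated comparisons do not use it. At exact 5:5 the cost is a standard error about 13% too large (3% to 27%) and, for an assumed 1 SD effect with categories 1 SD apart, power of 0.46 instead of 0.56. With unequal cells the estimate can also shift by chance, with medication intake the more exposed outcome. All these sizes depend on an assumed category difference, and the power figures on an assumed effect as well.

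The gap in 4.3 is secondary. It is certain that no procedure is written out; how far the cells depart from 5:5 is not known. The pilot's size limits the consequences, but the remedy is cheap enough to be worth making.

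**What to change.** **Analysis.** Add opioid-history category as a factor in the SAP's pain model, entered so that it acts on the contrast tested (with time as well, if the test is arm by time). Use a category-stratified rank test (van Elteren) for medication intake. State whether SUD in the SAP means the protocol's methadone/Subutex category. If outcome data have already been analysed, keep the stated analyses as reported and present the adjusted ones as clearly labelled post hoc sensitivity analyses.

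Cost: no patients or staff. In a woman-level analysis the factor takes one between-woman degree of freedom (18 to 17), moving the t critical value from 2.101 to 2.110, or 0.4%.

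**Allocation, if complete.** State the method actually used and report the TENS and control counts in each category. Cost: one sentence and one small table.

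**Allocation, if still open.** State in 4.3 that each category has its own concealed list in permuted blocks of randomly varying size 2 and 4, extended past 10 so that any replacement can be allocated. Say whether women who withdraw are replaced, since 4.7 B destroys their data and the analysed cells can differ from those allocated. Cost: two lists and some predictability, limited by concealment and varying block size. Lists forced to close at 5:5 would guarantee the cells, but would make the tenth assignment predictable and leave no places for replacements.
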